#### **4.3 Operational (logistical) and Trial Management monitoring of participants**

The reporting of the study will follow the guidelines set by CONSORT (2001) and extension to cluster randomised trial update statement (BMJ 2012). The report will detail the design, conduct, analysis and results of the data. This report will be supported by the tables, plots and flow diagrams that have been included in a separate document and signposted here.

##### **4.3.1 Recruitment of participants**

- Participants recruited within each general practice from the GP list size to the point of randomisation.
- Participants recruited within each general practice from the point of randomisation to end of intervention.
- Participants recruited within each intervention from the GP list size to the point of randomisation.

- Participants recruited within each intervention from the randomisation to the end of the intervention.
- A recruitment graph will show the number of participants recruited in randomised GP Practices over the entire study period.

#### 4.3.2 Intervention Phase

The flow of participants by treatment arm using the CONSORT diagram.

The number of participants in the balance screener risk categorisation by each intervention arm.

#### 4.3.3 Treatment received

For the MFFP+ advice arm, 'treatment received' is when the participants have had an MFFP assessment. They may then be referred on for additional treatments following this assessment.

For the Exercise + advice arm, 'treatment received' is when the participants have had their first assessment.

#### 4.3.4 Compliance/adherence

Treatment received: for the MFFP+ advice arm, 'treatment received' is when subgroups of eligible participants referred for the MFFP intervention have received their falls assessment.

We will tabulate the summary statistics of the number of participants who complied with the active interventions. Extent of "adherence" varies by intervention arm. This table will show the number of who attended 1 session, 2 sessions, 3 sessions and so on. Thus for MFFP, participants are only invited to attend one falls assessment therefore this counts as 1 session only (although with potential for onward referral for other specialist treatment but we count 1 appointment as assessment completed). For the Exercise+advice intervention arm, this is a recommended 6 month supported programme. We have start date and discharge

date for exercise on the main PreFIT database, thus can look at “exposure” by number/type of contacts.

#### 4.3.5 Follow-up

We will tabulate number of participants that were followed-up at each of the time points (4, 8 and 12 and 18 months).

#### 4.3.6 Violations or deviation from the protocol

- Protocol violators/deviators will fall into one of the following categories.
  - (i) Participants who receive an intervention different from that allocated;
  - (ii) Withdrawals;
  - (iii) Ineligible participants – any participant who was ineligible but subsequently received treatment in the randomised general practice.

## 5. OUTCOMES OF THE TRIAL

OUTCOMES	TIME POINT collected at	SCORING
Primary outcome		
Fall related fractures	Over the 18 months (Baseline, 4, 8, 12 and 18 months).	Fall fracture rates (per person per month observation) This will be obtained by estimating the rate over 18 months and fractioning this as a monthly rate
Secondary outcomes		
Additional fracture parameters		
 
• Proportion (and number) of people sustaining at least one fracture over the study period will be obtained. Thus, the derived variable will be binary (patient with at least one fracture =1/ no fracture =0).
 
• Time to first fracture
 
• Fracture rates and proportions for data extending beyond 18 months
 

Falls (CRF)	Over the 18 months (Baseline, 4, 8, 12 and 18 months)	
 
• Fall rates (per person per month observation)
 
• Proportion (and number) of people sustaining at least one fall over the study period.
 

Falls (Diary)		

Analysed at 4, 8, 12 For sensitivity analyses only	Baseline, 4, 8, 12 months	
 
• Fall rate (per person per month observation)
 
• Proportion (number) of people sustaining at least one fall
 

Frailty Strawbridge Questionnaire	Baseline and 18 months	
To summarise, the frailty questionnaire is Strawbridge 1998 with the four domains: physical, nutritional, cognitive and sensory. The score of this based on a 4 –point ordinal scale (rarely or never / sometimes /often /very often).
 
We will analyse overall and sub-domain scores

Mobility	Baseline, 4, 8, 12 and 18 months	Questions on difficulty in balancing on level surface, ability to walk outside of the house and average time spent walking.
EQ-5D	Baseline, 4, 8, 12 and 18 months	Evaluates patients QOL based on 5 dimensions converted into a single summary score (range: -0.57 to 0 (death) to 1 (perfect health state)).The ED-5D will be scored using the devised algorithm (EuroQol Group, 1990) and summarised as detailed in the User Guide (EuroQol Group, 2005).
SF-12	Baseline, 4, 8, 12 and 18 months	Scoring of the SF-12 will be carried out using ‘the SF-12v2- How to Score version 2 of the SF-12 Health Survey’ manual (Ware et al.1996).
Predictor variables		

Clock test	Baseline	Simple scoring system used e.g. 6 point scale of Shua-Haim et al. 1996: (1) Approx. drawing of clock face; (2) Presence of numbers in sequence; (3) Correct spatial arrangement of numbers; (4) Presence of clock hands; (5) Hands showing approx correct time; (6) Hands depicting the exact time
------------	----------	--

## **6. STATISTICAL ASPECTS**

The statistical analyses will be carried out using SAS (version 9.13).

All statistical tests will be two-sided and performed at the 5% significance level.

### **6.1 Analysis Populations**

Two populations of interest here are:

#### **6.1.1 Intention to treat (ITT) analysis (all patients who were recruited in the randomised GP practice regardless of falls risk)**

An ITT analysis would measure something more important than intervention efficacy, namely intervention policy. That is, it tests whether it is better to screen and then *prescribe* one of the experimental interventions to those at high risk rather than providing advice only (i.e. an ‘as-randomised analysis’ or intention to treat (ITT) compares the outcomes of participants by assigned group). The ITT effect is the effect of treatment assignment rather than the effect of treatment taken (often called ‘effectiveness’ as opposed to ‘efficacy’). A full ‘Intention-to-treat’ analysis is only possible when complete outcome data are available for all patients. One of the main reasons for advocating ITT analysis is that it gives an estimate as would be in the ‘real world’ and it also maintains the baseline comparability achieved by the randomisation process. If the initial random assignment is undermined, then confounding can be introduced and the internal validity of the results is consequently questionable.

The PREFIT trial consists of three intervention arms:

- 1) Advice only;
- 2) Advice, screening and exercise;
- 3) Advice, screening and MFFP.

Analysis will be at two levels:

- a. We will compare between the advice only and exercise arm, and separately, the advice only and MFFP arm.
- b. If there is evidence of a statistically or clinically important difference in either of the comparisons with advice only, we will then proceed to test exercise versus MFFP head to head, recognising that this comparison potentially has less power if both interventions were effective.

### 6.1.2 Nested Intention to treat

In a nested analysis we will present our finding just for those at intermediate/high risk of falling. We will establish the risk score of falling, using the baseline questions which are analogous to those on the Balance Screener but enable us to identify the at risk population across all three arms. The reason for using the baseline questionnaire is to ensure the risk score is available for all patients including those on the control arm as well as those on the interventions.

### 6.1.3 Allocation to the intervention (CACE analysis)

Taking the 'intermediate/high groups within each intervention arm, we will be able to establish the compliers and non-compliers.

Compliance will be defined as:

complier = Balancer screen returned and at risk of falling (i.e. categorised as high or intermediate) and had first assessment or balance screener returned and low risk of falling.  
Non-compliers = Balancer screen returned and at risk of falling (i.e. categorised as high or intermediate) but did not have first assessment or no Balance screener returned (although sent)

Using these we will be able to carry out the 'complier average causal effect' (CACE) analysis. The CACE analysis is the intervention effect among the true compliers; the difference in outcome between compliers in the treatment group and those controls who would have complied with intervention had they been randomised to the treatment group.

Complier average causal effect (CACE) is a measure of the causal effect of the intervention on the patients who receive it as intended by the original group allocation. Because it retains the randomisation assignment, it overcomes the problems related to per-protocol and on-treatment analysis.

CACE analysis makes two assumptions; the first is that members of the control group have the same probability of non-compliance as members of the intervention arm. If allocation is genuinely random, this statement must be accepted as true. This second is that merely being allocated to the intervention has no effect on outcome; i.e. outcomes are the same for participants who were not treated with one of the experimental intervention in both that intervention and advice only arms. Both of these assumptions appear reasonable for this trial.

Although this analysis has been specified, it is unclear at the onset whether it will be possible to carry it out due to model restrictions/assumptions. Hence we will explore these and compute fit these models, if possible.

## **6.2 Analysis Datasets**

The primary dataset for the analysis will be the observed dataset. The imputed dataset will be used for sensitivity analysis, if required.

### **6.2.1 Observed dataset**

This will comprise of all the data observed (including follow-up) with missing values. The data will also include a variable to indicate what treatment patients were randomised to and another variable to indicate what treatment they actually received so that the 'ITT' and 'CACE' analyses can be implemented.

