#### *6.3.2. Outcomes*

##### *6.3.2.1 Covariates to adjust in the statistical models*

The covariates that will be used to adjust for in the statistical models will be corresponding baseline variable, deprivation score (for the GP practice), age and gender.

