##### *6.3.2.2 Primary outcome*

Fracture rate (per person per month) observation has a skewed distribution (heavy skewed in favour of zeros). We will explore the possible models that may account for this skew: (a) Poisson model; (b) zero inflated Poisson model; (c) negative binomial; (d) zero inflated negative model.

For the fracture rate (per person per month observation), we will assess this over the 18 months, using an 'offset' variable in the appropriate model, and also incorporate the general practice variable as the random effect.

Proportion of patients having at least one fracture, will be analysed using logistic regression models, with the random effect as general practice. The adjusted analysis will incorporate the appropriate covariates (as stated above).

Time to first fracture will be assessed using survival analysis methods.

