#### 6.3.2.5. Secondary outcome: EQ 5D

The items of the EQ-5D will be summarised for each of the interventions and time-points.

The EQ -5D score will be summarised using mean, standard deviation, median and range values. The mean difference (and the 95% of the mean difference) between treatment arms will be reported. Both adjusted and unadjusted random effect linear regression models will be fitted to the data.

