#### 6.3.2.7. Secondary outcome: Strawbridge Questionnaire

For each of the four domains of the Strawbridge Questionnaire we will summarise the data into will be summarised into binary categories (rarely or never/sometimes) and (often/very often).

Both adjusted and unadjusted random effect logistics regression models will be fitted to the data.

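### The adjusted models run on unfilled data, so participants with a known outcome but a blank baseline value would fall out, and adjusted and unadjusted results could describe different people

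*SAP*

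**What the plan says.** - **Dataset.** SAP 6.2: "The primary dataset for the analysis will be the observed dataset. The imputed dataset will be used for sensitivity analysis, if required". SAP 6.2.1 adds: "This will comprise of all the data observed (including follow-up) with missing values".
- **Covariates.** SAP 6.3.2.1 states that the adjustment variables "will be corresponding baseline variable, deprivation score (for the GP practice), age and gender".
- **Adjusted and unadjusted pairs.** For EQ-5D (6.3.2.5), with the same sentence for SF-12 (6.3.2.6): "Both adjusted and unadjusted random effect linear regression models will be fitted to the data". For Strawbridge (6.3.2.7): "Both adjusted and unadjusted random effect logistics regression models will be fitted to the data". None of these sections names a common set of participants.
- **Fractures and falls.** SAP 6.3.2.2: "The adjusted analysis will incorporate the appropriate covariates (as stated above"). Falls (6.3.2.3) follow the approach for the primary outcome. Mobility is left to suitable regression models.
- **Population.** The ITT population in SAP 6.1.1 is "all patients who were recruited in the randomised GP practice regardless of falls risk".
- **Missing data.** SAP 6.2.2 summarises missingness outcome by outcome. If that proves problematic, imputation follows as a sensitivity analysis. The section recognises that participants or staff may leave fields blank, but gives no rule for a blank baseline covariate in the main models.

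**The concern.** A regression procedure ordinarily omits any record with a missing covariate. With the dataset left unfilled and the baseline value in the model, a participant who answered the EQ-5D at 18 months but left it blank at baseline counts in the unadjusted model and vanishes from the adjusted one.

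Two things are at stake. First, the adjusted analysis departs from the ITT population for an avoidable reason. SAP 6.1.1 itself ties a full ITT analysis to complete outcome data, and these people's outcome is known. Second, where adjusted and unadjusted estimates differ, a reader cannot tell how much is due to adjustment and how much to a change of sample. Some precision is also lost, but that is the lesser matter.

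**Working it through.** **Which outcomes are reached**

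| Outcome | Corresponding baseline value (SAP section 5) | Effect |
|---|---|---|
| EQ-5D, SF-12, Strawbridge | Self-reported questionnaire | Adjusted model can lose people; the paired unadjusted model keeps them |
| Mobility, falls | Self-reported | Adjusted model can lose people; no adjusted/unadjusted pair is spelled out |
| Fractures | Not identified | Little affected if only age, gender and practice deprivation are used |

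**Inputs.** SAP 2.7 gives 150 participants per practice, 60 practices, 10% loss to follow-up and an ICC of 0.001 to 0.003 (for fractures). Those with an outcome: 0.9 × 150 = 135 per practice, and 0.9 × 9,000 = 8,100 in all. The SAP gives no share *f* of these who lack the baseline value and no ICC for questionnaire outcomes; both are assumed below.

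**The plan's own figures.** The SAP has no figure for this point, but the inputs borrowed from 2.7 are coherent. For 6% against 4%, 80% power, two-sided 5%, pooled variance:

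n = [1.960·√(2 × 0.05 × 0.95) + 0.842·√(0.06 × 0.94 + 0.04 × 0.96)]² / 0.02² ≈ 1,863 per arm, against 1,900 stated.

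The design effect 1 + 149 × ICC is 1.149 to 1.447, so 5,700 becomes about 6,549 to 8,248. The stated 7,800 lies inside. Nothing here disputes those figures.

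**People lost.** 8,100 × *f* = 81, 405 and 810 at *f* = 1%, 5% and 10%.

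**Interval widening relative to complete baseline data.** Losing people within practices leaves the between-practice variance unchanged. With m = 135 and m′ = 135(1 − *f*):

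ratio = √{ [(1 + (m′ − 1)·ICC)/m′] / [(1 + (m − 1)·ICC)/m] }

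At *f* = 10%, m′ = 121.5:
- ICC 0.001: √[(1.1205/121.5)/(1.134/135)] = 1.048
- ICC 0.003: √[(1.3615/121.5)/(1.402/135)] = 1.039

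| *f* | ICC 0.001 | ICC 0.003 |
|---|---|---|
| 2% | 0.9% | 0.7% |
| 5% | 2.3% | 1.9% |
| 10% | 4.8% | 3.9% |
| 15% | 7.5% | 6.1% |

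At an assumed ICC of 0.01 the last two rows become 2.3% and 3.7%.

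**Net gain from filling.** People given a mean-filled baseline contribute their full outcome variance, not the residual variance 1 − r². For a linear model, ignoring clustering, with r the assumed baseline–outcome correlation, the interval-width ratio of dropping to filling is

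√{ (1 − r²) / [(1 − *f*)·((1 − *f*)(1 − r²) + *f*)] }

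At *f* = 10%:
- r = 0.5: √(0.75/0.6975) = 1.037, a gain of 3.7%
- r = 0.6: √(0.64/0.6084) = 1.026, a gain of 2.6%
- r = 0.7: √(0.51/0.5031) = 1.007, a gain of 0.7%
- r = 0.8: √(0.36/0.3816) = 0.971, so filling gives an interval about 3% *wider* than dropping

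The break-even is where 1 − r² = (1 − *f*)/(2 − *f*) = 0.9/1.9 = 0.474, that is r ≈ 0.73.

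**The case against.** The strongest reply is that the SAP nowhere orders anyone to be dropped, and that 6.2.2 already acknowledges blank fields without confining them to outcomes and names multiple imputation and chained equations, which can fill covariates. The first part is correct: the loss is an inference from the unfilled dataset, the covariate list and ordinary software behaviour. The second part helps only in part. Imputation there is conditional, is set off by a review of outcome missingness, and is a sensitivity analysis, so the main adjusted model is unchanged.

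It may also be said that 6.1.2 expects the baseline questionnaire to give a risk score for every patient. That explains why the questionnaire is the chosen source across all three arms; it does not show that every item was completed.

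Several stronger readings are tempting and are not supported:

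- *Collected outcome data are thrown away altogether.* For EQ-5D, SF-12 and Strawbridge the planned unadjusted model still uses every observed outcome.
- *The primary fracture result is compromised.* This does not follow if age, gender and practice deprivation are the only covariates and are near complete (an assumption).
- *Those lost are mainly the frailer participants.* The SAP has no information on who leaves items blank.
- *Intervals widen by 1/√(1 − f), about 5% at 10% and 8% at 15%.* That treats participants as independent, and it does not measure what filling would recover.

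The caution about mean-filling also stands. It does not suit categorical baselines, and in logistic models it mixes odds ratios that are conditional on the covariate with ones that are not.

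**Conclusion.** The point holds as a minor one, confined to the adjusted models for questionnaire outcomes and falls. As planned, ITT members with an observed outcome and a blank baseline value would leave those models, and for EQ-5D, SF-12 and Strawbridge the adjusted and unadjusted results would then describe different people.

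The size is unknown because the SAP states no missingness rate. At an assumed 10%, the widening is 3.9 to 4.8%, provided the fracture ICC range carries over to these outcomes. The net precision gain from filling is smaller and is gone by a correlation a little above 0.7. The case for change therefore rests on keeping the ITT set and a common sample, not on precision.

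**What to change.** Add to SAP 6.3.2.1:

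> Participants with an observed outcome and a missing baseline covariate stay in the adjusted model. The baseline value is filled without reference to arm: the overall mean plus a missing-value indicator for continuous scores, and a separate missing category for categorical items. Adjusted and unadjusted models are fitted to the same participants and the number in each is reported. A complete-case adjusted model is a sensitivity analysis.

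This relies on baseline data being collected at enrolment, which SAP 2.4 places before the practice is randomised. If some baseline forms came later, the SAP should say so.

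The cost is one short paragraph and a few lines of code, with no new data. The downsides are less precision gain from the covariate among those filled in and, in logistic models, a slight shift in the adjusted odds ratio. The complete-case sensitivity analysis would make both visible.

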### **6.2.2 Imputed dataset (missing data)**

We will assess the extent of missingness for each of the outcomes by summarising the data. If missingness is problematic, we will then compute a sensitivity analysis, namely imputation analysis, to assess the effect of the missingness.

If imputation methods are required for the primary outcome, we will explore the possibility of implementing these. However, due to distributional constraints, we may not be able to adequately model the missingness for the primary outcome.

Data can be missing in fields in two situations: (a) when it is not applicable (validly missing) and (b) it can be missing due to patient/health professional leaving fields blank when they should have completed the question with an answer (invalidly missing). The latter will be examined for the different data mechanisms (MAR - missing at random; NMAR - not missing at random; MCAR - missing completely at random) and we will assess whether multiple imputation is viable. In the case where multiple imputation can be used and the data can be assumed normal, multivariate methods will be applied. In the case where one cannot assume a distribution of the data, the ICE (imputation by chain equations) will be used.

## **6.3 Statistical Analysis**

### *Comparison of those decline/excluded with those who were consented*

Where possible, appropriate variables will be summarised for these to sub-population to ensure that the groups are comparable and representative of the entire population.

#### *6.3.1 Demographic and baseline*

These data will be summarised using mean, standard deviation, median and range values as appropriate. In the case of the categorical assessments, the number of patients (together with the percentage) will be specified.

#### *6.3.2. Outcomes*

##### *6.3.2.1 Covariates to adjust in the statistical models*

The covariates that will be used to adjust for in the statistical models will be corresponding baseline variable, deprivation score (for the GP practice), age and gender.

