## 2.4 Randomisation

- Unit of randomisation is the general practice.
- The Warwick Clinical Trials Unit programming team will generate the randomisation. The clusters are allocated to the interventions by the data management team
- General practices will be randomly allocated in blocks of three with one of the three trial treatments. There is no stratification and the method of randomisation is minimisation by general practice.
- Practices will be randomised simultaneously when the initial record searches have been completed and the sample identified and enrolled (400 participants screened and contacted to obtain a sample of 150 enrolled trial participants) at all three practices in each block.

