### **4.1 Operational (logistical) and Trial Management of Regions**

- There are 5 regions recruiting participants to the PRE-Fit trial: Devon, Warwickshire / Herefordshire, Worcestershire, Cambridge and Newcastle.
- Within the regions are the general practices. These general practices are randomised in clusters of 3, and within each general practice all participants are allocated to the randomised intervention.

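### Practices are randomised in blocks of three, but block is missing from the analysis models, so standard errors may be somewhat too large

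*SAP*

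**What the plan says.** Section 2.4 describes the allocation: "General practices will be randomly allocated in blocks of three with one of the three trial treatments". The practices of a block enter together: "Practices will be randomised simultaneously when the initial record searches have been completed and the sample identified and enrolled", a condition that must be met at all three practices. Section 4.1 repeats the grouping: "Within the regions are the general practices. These general practices are randomised in clusters of 3". Section 2.4 also says: "There is no stratification and the method of randomisation is minimisation by general practice". No minimisation factor is named.

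On the analysis side, section 6.3.2.1 gives the adjustment set as "corresponding baseline variable, deprivation score (for the GP practice), age and gender". For the fracture rate, section 6.3.2.2 will "also incorporate the general practice variable as the random effect". The proportion with at least one fracture "will be analysed using logistic regression models, with the random effect as general practice". Neither section mentions the randomisation block.

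**The concern.** One practice per arm in each simultaneously randomised triplet is a randomised block design with practices as units. The three practices of a block share a randomisation date. If the triplets were formed locally, they share a locality as well. Fracture rates and the recording of fractures may differ between blocks for these reasons.

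Blocking removes such differences from the treatment contrast itself, because each arm appears once in every block. A model with practice but no block still counts them as practice-to-practice noise. The reported standard error then exceeds the true sampling error. Confidence intervals are too wide, the test rejects a true null less often than 5%, and some power is lost.

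Section 2.4 adds a second difficulty. Because its terms are not reconciled, a reader cannot tell which allocation factors the model ought to carry.

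**Working it through.** **1. The plan's own figures (SAP section 2.7).** For 6% against 4%, two-sided 5%, 80% power, pooled variance under the null and no continuity correction:

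n = [1.96 × √(2 × 0.05 × 0.95) + 0.8416 × √(0.06 × 0.94 + 0.04 × 0.96)]² / 0.02² = 1,863 per arm, within 3% of the stated 1,900.

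The design effect 1 + 149 × ICC takes 1,900 to 2,183 at ICC 0.001 and to 2,749 at 0.003. The stated 2,600 corresponds to an ICC of about 0.0025, inside the stated range. Then 7,800 / 0.9 = 8,667, rounded up to 9,000 = 60 × 150. The figures reproduce.

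**2. Inputs for the block question.**
- Blocks: 60 / 3 = 20, so 20 practices per arm.
- Analysed per practice: 150 × 0.9 = 135, or 2,700 per arm.
- Mean risk 5%, total variance 0.05 × 0.95 = 0.0475, difference 0.02.
- ICC 0.001 to 0.003 (section 2.7).
- f, the share of between-practice variance that lies between blocks. The SAP does not give it, so it is taken over its whole range, 0 to 1.

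**3. Formulas.** Let B = ICC × 0.0475 and W = (1 − ICC) × 0.0475.
- Variance assumed when block is omitted: (2/20) × (B + W/135).
- True variance of the contrast: (2/20) × ((1 − f) × B + W/135).
- r = square root of their ratio, the factor by which the SE is overstated.
- Type I error when block is omitted: 2 × (1 − Φ(1.96 r)).
- Power: Φ(0.02/SE_true − 1.96 r) without block, Φ(0.02/SE_true − 1.96) with block.

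**4. One case in full: ICC 0.003, f = 0.5.** B = 0.0001425 and W/135 = 0.0003508. The assumed variance is 0.1 × 0.0004933 (SE 0.00702). The true variance is 0.1 × 0.0004221 (SE 0.00650). So r = 1.081. Power without block is Φ(3.079 − 2.119) = 83.1%; with block it is Φ(3.079 − 1.960) = 86.8%.

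**5. Results.**

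| ICC | f | r | Type I error, block omitted | Power without block | Power with block | Loss (points) |
|---|---|---|---|---|---|---|
| 0.001 | 0 | 1.000 | 0.050 | 88.6% | 88.6% | 0 |
| 0.001 | 0.5 | 1.031 | 0.043 | 89.3% | 90.4% | 1.1 |
| 0.001 | 1 | 1.065 | 0.037 | 90.1% | 92.1% | 2.0 |
| 0.003 | 0 | 1.000 | 0.050 | 81.3% | 81.3% | 0 |
| 0.003 | 0.5 | 1.081 | 0.034 | 83.1% | 86.8% | 3.7 |
| 0.003 | 1 | 1.186 | 0.020 | 85.4% | 92.2% | 6.8 |

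**6. Simulation.** In 20,000 runs per setting, practice-level proportions were compared with and without pairing by block. With block omitted, type I error was 0.045 (ICC 0.001) and 0.034 (ICC 0.003) at f = 0.5, and 0.035 and 0.022 at f = 1. With block used it was between 0.048 and 0.050 in these four settings.

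**The case against.** The strongest reply is that the main design feature is already handled. The practice is the unit of randomisation and is a random effect in the rate and logistic fracture models. What remains is conservative, so a positive result would not be undermined. Practice deprivation is already a covariate and may absorb some of the variation in question. If blocks explain nothing, nothing is gained. A second variance component at such small ICCs may also be hard to estimate, particularly in the zero-inflated candidate models. All of this stands. It limits the size of the point, but it does not explain why the grouping used to allocate is absent from the model.

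A reader might go further in four ways that the document does not support.
- *The standard errors ignore the design, or are too small.* Only the blocking is unmodelled, and that error makes them too large. This answer covers the rate and logistic models; section 6.3.2.2 states no clustering term for time to first fracture.
- *Region is an omitted randomisation factor.* Section 4.1 places practices within regions but does not say that a block lies within one region, and section 2.4 says there was no stratification.
- *Power would rise from 80% to well above 85%.* That takes the top ICC and a large block share. Even at ICC 0.003 and f = 0.5, setting 86.8% against the 81.3% at f = 0 overstates the gain. The test without block also benefits from the smaller true variance, so the right comparison is with 83.1%. With 2,700 analysed per arm, power is near 80% only at the top of the ICC range.
- *Blocks and minimisation are incompatible.* The order of arms within each triplet could be chosen to reduce imbalance against blocks already allocated, and the factors may be named in the protocol. Section 2.4 is unclear, but it does not describe something impossible.

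**Conclusion.** The point holds as one of efficiency and consistency. By the SAP's own account practices are allocated in triplets, and its models do not carry the triplet. The cost lies between nothing and the f = 1 rows of the table, and is modest at a middling block share.

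These sizes rest on an unknown share f, on complete blocks with equal practice sizes, and on a normal approximation to a difference in proportions. The primary analysis is a count model for the fracture rate, so the figures indicate scale and do not predict that model's exact power. They also make no allowance for what the deprivation covariate might absorb.

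Separately, section 2.4 should be clarified whatever the precision effect, because the right adjustment set depends on what was actually done.

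**What to change.** In sections 6.3.2.1 and 6.3.2.2, add randomisation block as a random effect alongside practice, and carry it through to the secondary models. Suggested wording: *Models will include random effects for randomisation block and for general practice within block. If the block variance is estimated as zero, or the model does not converge, the block term will be dropped and this will be reported.* The rule should be fixed before unblinding and should not depend on the treatment estimate.

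Include region as a design term only if blocks were formed within regions; otherwise it is an optional prognostic covariate.

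In section 2.4, reconcile the blocks of three, the absence of stratification and the minimisation into one account of what was done. If practices were minimised on any factor, name it and adjust for it.

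The cost is SAP text and one more variance component, which may be estimated near zero or be hard to fit in the zero-inflated models. Block as a fixed effect would use 20 − 1 = 19 degrees of freedom among 60 practices, so the random effect is preferable.
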